9.5 STUDY SIZE

A preliminary feasibility assessment of the most recent EMR data indicates the presence of 2,499 patients newly starting on an IPF treatment (Table 1). 64% of patients are 40 years or above, of which 76% had at least one pulmonary function test. An early feasibility assessment estimated that about 10,000 IPF patients were not treated with antifibrotics.

Considering the orphan nature of IPF and recent FDA approval of these two drugs (within last three years), the EMR database is a good source to extract such a population as it continues to grow. The IPF patients counts are reflective of national estimates (6.8–8.8 per 100,000; <0.01%). The availability of patients should provide sufficient sample to estimate standardized differences in patient characteristics between three cohorts.

Table 1. Preliminary Patient Counts (will vary once study selection criteria are applied, as outlined in Section 9.2)

	Characteristics	Number of patients
1	Evidence of IPF treatment (pirfenidone or nintedanib) between October 1, 2014 to March 30, 2018), first date is index	2,750
2	In #1 with ≥ 1 EMR before index date	2,508
3	In #2 with no evidence of pirfenidone or nintedanib before index date	2,499
4	In #3 with diagnosis of IPF (ICD-9-CM codes 516.3x, 515, or ICD-10-CM codes J84.112) before index date	2,061
5a	In #4 and with prescription for (mutually exclusive): Pirfenidone only Nintedanib only Both Pirfenidone and Nintedanib	1,627 868 615 144
5b	In #4 and age ≥ 40 years	1,623
5c	In #4 with at least one PFT observations (FEV1, FVC, TLC, Oxygen saturation, OR DCCO) (with non-missing test results) BEFORE index	1,231
6a	In 5c with at least one oxygen saturation value	1,150
6b	In 5c with at least one DCCO value	293

Characteristics		Number of patients
6c	In 5c with at least one TLC value	217
6d	In 5c with at least one FEV/FVC value	627

9.6 DATA MANAGEMENT

The study will involve use of de-identified EMR data files. Data obtained from the EMR files will be imported into and maintained in a SAS® data analysis file. Tabulation of summary statistics, graphical presentations, and statistical analysis will be performed using SAS® software. The data files are statistically de-identified and don't contain any personal identifiable information. The data are not subject to oversight by the Institutional Review Board (IRB); however, IRB exemption will be obtained. All files will be stored on a secure server and access will be limited to the project team and other authorized personnel.

After applying study inclusion and exclusion criteria, a study database will be created with all of the necessary variables to perform statistical analysis. The aggregated data (in form of counts, %, mean, median, etc.) will be shared with BI at each stage of data programming. The data abstraction will be monitored continuously for quality control purposes, and final results will only be reported after thorough review of programming codes by internal staff members as well as external consultants.

9.7 DATA ANALYSIS

We will ensure internal validity by measuring key study measures and outcomes using a standardized process. All codes and definitions will be reviewed by BI, and any modifications to them can be made prior to delivering the final protocol document.

With respect to external validity, IPF patients will be identified using ICD-9 or ICD-10 diagnosis codes that have been used in previously published studies.¹¹⁻¹³ Pirfenidone and nintedanib, as well as other treatments of interest in this study, will be identified by RxNorm (where available) and a search of drug names (including possible variants of the name). Although there are some potential limitations with generalizability of the study findings, the current study is being conducted using an internal database that contains information on 42 million active patients in the US. Therefore, the findings from our study will have broad generalizability to IPF patients, ensuring appropriate external validity.

9.7.1 Main analysis

For the primary objective, baseline patient characteristics will be described using descriptive analysis, i.e. described as counts and percentages for categorical variables (e.g. gender, race, comorbidities, treatments, diagnostic tests performed) and measures of central tendency (mean, median, SD, and min/max) for continuous variables (e.g., age, lab measures values, BMI). Differences between the cohorts will be assessed using ASD, where an ASD of at least 10% will be considered a meaningful difference.²² Patients with missing data will be reported as missing and excluded from the comparison for the missing variable.

For continuous variables, the standardized differences will be calculated as

$$d = \frac{(\bar{X}_1 - \bar{X}_2)}{\sqrt{\frac{s_1^2 + s_2^2}{2}}}$$

Where \bar{X} denote sample means in each exposure cohort, and s denotes sample variances.

For categorical variables, the standardized differences will be calculated as

$$d = \frac{(p_1 - p_2)}{\sqrt{\frac{[p_1(1 - p_1) + p_2(1 - p_2)]}{2}}}$$

Where p denotes proportion of a binary baseline variable in the two exposure cohorts.

The confidence intervals (CIs) for standardized differences will also be calculated as defined below:

$$95\% CI = d \pm 1.96 \times \sigma [d]$$

$$\text{where, } \sigma [d] = \sqrt{\frac{n_1 + n_2}{n_1 \times n_2} + \frac{d^2}{2(n_1 + n_2)}},$$

Where n_i denotes sample sizes of each exposure cohort.

Bivariate statistical significance tests such as Chi-square test for categorical variables and Wilcoxon rank sum test or t-test for continuous variables (depending on distribution of data) will also be performed to compare differences in baseline characteristics between the three cohorts. In addition to standardized differences, p-value in comparing characteristics between the three cohorts will also be reported to help identify “key drivers” associated with treatment selection.

For the second objective, the probabilities of receiving one treatment over another (or nintedanib or pirfenidone vs. untreated) will be tested by propensity scores (PS) and using multivariable logistic regression (possibly with stepwise selection) after controlling for key baseline characteristics (selected based on significance in bivariate analysis or face validity, e.g. age). The similarities and differences between the exposure cohorts will be assessed using balance diagnostics tests (e.g., graphical distribution of overlap between propensity scores of two cohorts (histograms, boxplots), percentage of sample matched, Pearson’s correlation coefficient, standardized differences, density estimates, c-statistics, receiver operating characteristic [ROC] curves). Ninety-five percent confidence intervals will be calculated for key parameters. Statistical tests will be two-sided, with α -level of 0.05 for statistical significance.

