	antifibrotic treatment between October 1, 2014 and April 30, 2018. Patients will be divided into three mutually exclusive cohorts: (1) nintedanib initiators; (2) pirfenidone initiators; and (3) control cohort who received no prescription antifibrotic treatment during selection window.										
Variables:	The following demographic and clinical characteristics as well as medical interventions for IPF during the 12-month baseline period (pre-treatment) will be evaluated and compared between cohorts 
 Demographic characteristics (e.g., age, gender, race/ethnicity, geographic region, insurance type) Clinical characteristics (e.g., selected comorbidities, baseline weight and body mass index [BMI], blood pressure, smoking status, laboratory measures, pulmonary function tests) Pharmacological interventions (e.g., index medication dose, time from the earliest diagnosis of IPF to index medication, other IPF treatments, bronchodilators, corticosteroids) Non-pharmacological interventions (e.g., surgical procedures, supportive therapies, diagnostic procedures) 										
Data sources:	GE Centricity EMR database from October 2013 to April 2018										
Study size:	A preliminary analysis identified 868 IPF patients with pirfenidone, 615 patients with nintedanib, and about 10,000 untreated patients.										
Data analysis:	Patient demographic and clinical characteristics will be described using descriptive analyses. Counts and percentages for categorical variables and measures of central tendency (mean, median, standard deviation [SD], and min/max) for continuous variables will be reported. Differences between the treatment cohorts (compared to each other and to untreated patients) will be assessed using absolute standardized differences and p-values. The probabilities of receiving one treatment over another will be tested by propensity scores and using multivariable logistic regression adjusted for key baseline characteristics. The similarities and differences between two treatment cohorts will be assessed using balance diagnostics tests. A stratified descriptive analysis will also be conducted at different time points to assess if the characteristics of the two exposures changes over time.										

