9.3.2.2 Secondary outcomes

The secondary outcomes will be the probabilities (propensity scores) of receiving one treatment over another (or probability of receiving antifibrotic treatment) between the following cohorts:

- Nintedanib vs. pirfenidone
- Treated patients (i.e., nintedanib or pirfenidone) vs. untreated

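### The propensity score is a secondary outcome compared between the same cohorts used to fit it, so its apparent separation is biased upward and the plan has no correction

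*Combined protocol and SAP*

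**What the plan says.** Section 9.3.2.2 states: "The secondary outcomes will be the probabilities (propensity scores) of receiving one treatment over another (or probability of receiving antifibrotic treatment) between the following cohorts". Two comparisons follow: nintedanib vs pirfenidone, and "Treated patients (i.e., nintedanib or pirfenidone) vs. untreated". Section 9.1 also names the PS as the secondary endpoint.

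Section 9.7.1 says that these probabilities "will be tested by propensity scores (PS) and using multivariable logistic regression". Stepwise selection is allowed, and covariates are "selected based on significance in bivariate analysis or face validity, e.g. age". The cohorts are then compared by a list of example diagnostics that includes "graphical distribution of overlap between propensity scores of two cohorts", standardized differences, c-statistics and ROC curves. The paragraph closes with two-sided tests at 0.05.

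The 10% rule appears earlier in Section 9.7.1, under the primary objective: "Differences between the cohorts will be assessed using ASD, where an ASD of at least 10% will be considered a meaningful difference". The second-objective paragraph sets no cut-off for the PS and does not say whether its standardized differences are taken on the PS or on the covariates.

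The plan describes no sample split, cross-validation, optimism correction, permutation reference or global test, and gives no number of covariates for the PS model.

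**The concern.** A fitted PS is the combination of covariates that best separates the two cohorts in hand. Compared in the same patients, it shows some separation even when cohort membership is unrelated to every covariate, and the excess grows with the number of covariates. This is harmless when the PS is an adjustment tool. Here the PS is the result: Section 7 says the study will identify characteristics that drive treatment initiation by assessing the probability of treatment. Part of the reported separation would then be sampling noise, and it could be read as channelling.

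The problem does not need data-driven selection. It is present with a fixed list, and the screening that Section 9.7.1 permits adds to it.

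**Working it through.** The plan gives no error rate or expected separation for this outcome, so there is no figure to reproduce.

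**Inputs.** Cohort sizes are from the Abstract: "A preliminary analysis identified 868 IPF patients with pirfenidone, 615 patients with nintedanib, and about 10,000 untreated patients". Treated patients number 615 + 868 = 1,483. Alpha is 0.05 two-sided (Section 9.7.1). The number of covariates k is not stated, so a range is shown.

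**Null distribution, fixed covariates.** With identical cohorts, the in-sample standardized difference (ASD) of the fitted score is close to the Mahalanobis distance between the covariate means:

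- ASD² ≈ (1/n1 + 1/n2) × χ² with k degrees of freedom, so the root-mean-square ASD is √[k(1/n1 + 1/n2)].
- A two-sample test on the fitted PS has squared statistic ≈ χ² with k degrees of freedom but is referred to 3.84, the 1-df critical value. Its null rejection rate is P(χ²_k > 3.84).
- c-statistic ≈ Φ(ASD/√2).

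**Nintedanib vs pirfenidone.** 1/615 + 1/868 = 0.002778.

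| k | RMS ASD | Mean ASD | c-statistic | 0.05 test on PS rejects |
|---|---|---|---|---|
| 5 | √0.01389 = 0.118 | 0.11 | 0.53 | 57% |
| 10 | √0.02778 = 0.167 | 0.16 | 0.55 | 95% |
| 20 | √0.05556 = 0.236 | 0.23 | 0.57 | >99.9% |
| 40 | √0.1111 = 0.333 | 0.33 | 0.59 | about 100% |

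Null simulations with a logistic PS and a t-test agree. Rejection was 55–59% (k=5), 94–97% (k=10) and 100% (k=20 and 40). Mean ASD was 0.11, 0.16–0.17, 0.23–0.24 and 0.33–0.34.

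**Treated vs untreated.** 1/1,483 + 1/10,000 = 0.000774. The RMS ASD is √0.01549 = 0.12 (k=20) and √0.03097 = 0.18 (k=40). The bias in ASD is smaller here, but the rejection rate of a 0.05 test depends only on k and is the same as in the table.

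**If the 10% line were applied to the PS.** P(ASD ≥ 0.10) = P(χ²_k ≥ 0.01/(1/n1 + 1/n2)), with cut-offs 3.60 and 12.91.

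- Drug vs drug: 5.8% (k=1), 31% (k=3), 61% (k=5), 96% (k=10).
- Treated vs untreated: 2.4% (k=5), 23% (k=10), 88% (k=20).

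**With bivariate screening at p<0.05** (simulated, identical cohorts, 615 vs 868). With 60 candidates about 3 are selected, yet the mean in-sample ASD is 0.20. With 139 candidates, an approximate count of the Section 9.3.3 measures, about 7 are selected and the mean is 0.30–0.32. A short final model is therefore no protection.

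**Which remedies hold under the null.**

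- Likelihood-ratio test, fixed list: rejects in about 2–8%, around nominal.
- Likelihood-ratio test after screening on the full data: rejects in about 64–67% (20 candidates), 85% (40) and essentially 100% (100).
- Cross-fitted ASD with screening done once outside the folds: reaches 0.10 in about 30% (20 candidates) to 93–96% (100).
- Cross-fitted ASD with selection repeated inside each fold: reaches 0.10 in 2–7%.
- Selection and fitting in one half, comparison in the other: mean ASD about 0, c-statistic about 0.50, p<0.05 in 3–7%.
- Permutation reference for the in-sample ASD (10–50 fixed covariates): rejects in 3–5%.

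**The case against.** Several parts of the case on the other side stand.

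- A reader might infer that the plan would declare a meaningful difference on the PS almost every time. The documents do not support that. The 10% rule is written for baseline characteristics, and the standardized differences listed for the second objective may well be covariate-level.
- No t-test on the PS is specified. The wording says the probabilities will be tested and sets an alpha, which leaves such a test open without naming it. The named logistic regression is a legitimate route, and for a fixed list its likelihood-ratio test is close to nominal.
- The null c-statistics are modest. About 0.57 with 20 covariates would read as weak separation, so a reader should not infer that channelling would be concluded whatever the data.
- The rates depend on an unstated k and on preliminary counts that Table 1 says will change. With one to three covariates the problem is small.
- A reader might extend the point to the percentage of sample matched. The plan gives no matching ratio or denominator, so any ceiling on that figure would rest on assumptions, and it is not part of this point.

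What remains is that every in-sample measure of PS separation, with or without a threshold, is biased in one direction, and the plan does not correct it or say how the comparison will be judged. Section 9.3.3 lists far more than 20 measures, so a very small k is unlikely, though not excluded.

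**Conclusion.** The concern holds in this limited form. The secondary outcome is assessed in the cohorts that produced it, and the apparent separation is inflated by an amount that can be calculated for any k. For nintedanib vs pirfenidone the inflation in ASD is about 0.11 to 0.33 for 5 to 40 fixed noise covariates. For treated vs untreated it is about 0.12 to 0.18 for 20 to 40. Any 0.05 test applied directly to the fitted PS would be invalid with more than a few covariates.

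These figures assume the preliminary cohort sizes, covariates unrelated to cohort, and, for the rejection rates, that the PS itself is tested or held against 10%. The plan neither states nor rules out that use. The point affects how the secondary objective is interpreted. It does not touch the primary descriptive comparison of individual characteristics.

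**What to change.** In the second-objective paragraph of Section 9.7.1:

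1. State that the in-sample PS will not be tested between cohorts or read against 10% or p<0.05.
2. Report PS overlap, the PS standardized difference and the c-statistic from cross-fitted scores, where each patient is scored by a model fitted without that patient, or with bootstrap optimism correction. Repeat any bivariate or stepwise selection inside each fold or resample. Report the cross-fitted difference with its sign: with fixed noise covariates its absolute value reached 0.10 in 19–29% of null runs, mostly in the wrong direction.
3. Test the global question with a likelihood-ratio test only if the covariate list is fixed before the cohort comparisons are seen. Otherwise use a permutation test that reshuffles cohort labels and repeats the selection each time.

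The cost is analysis wording and a little more programming, with no new data. Reported separation will look somewhat smaller.

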Several clinical trials have been conducted to evaluate the efficacy and safety of these two emerging treatments. A recent systematic review and meta-analysis of ten randomized controlled trials showed that both pirfenidone and nintedanib reduced the progression of IPF in terms of FVC (forced vital capacity) decline and had similar safety profiles.⁹ However, only nintedanib significantly reduced the risk of all-cause and respiratory death. Pirfenidone and nintedanib also reduced the risk of a $\geq 10\%$ decline in FVC over 12 months, although only nintedanib protected against the risk of acute exacerbations.⁹

Patients selected into clinical trials usually present with fewer comorbidities, fall between certain age limits, and the severity of their disease is defined.¹⁰ Therefore, clinical trial populations do not always reflect the entire population affected by IPF in the real-world setting. Understanding patient characteristics is essential when assessing the real-world effectiveness of a treatment. Unlike being randomly assigned to a treatment in clinical trials, patients in the real world may choose between similar treatments based on existing comorbidities and concomitant medications, differentiating the effectiveness of the medications in certain patients. When comparing nintedanib and pirfenidone, it is therefore important to understand the differences in clinical characteristics of patients who are prescribed nintedanib compared to patients who are prescribed pirfenidone, and how these patients compare to IPF patients who do not receive antifibrotic treatment.

In order to help identify the profile of patients and specific characteristics associated with initiating treatment for IPF, BI is conducting a retrospective database study to understand differences in characteristics of patients who are prescribed pirfenidone or nintedanib, and those who do not receive a prescription for an antifibrotic treatment. This study will also help identify patient characteristics driving the initiation of nintedanib or pirfenidone by assessing the probability of receiving the treatments.

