9. RESEARCH METHODS

9.1 STUDY DESIGN

To address the objectives above, this retrospective database study will use a new user cohort design, where cohorts are defined based on the exposures of interest (i.e., prescription for nintedanib or pirfenidone or no antifibrotic treatment). The study population will consist of the following three mutually exclusive cohorts:

1. Nintedanib initiators, consisting of adult IPF patients who newly initiated nintedanib treatment
2. Pirfenidone initiators, consisting of adult IPF patients who newly initiated pirfenidone treatment
3. Untreated cohort, consisting of adult IPF patients without any prescription for antifibrotic treatment (i.e., no prescription for nintedanib nor pirfenidone)

The primary study endpoint is the absolute standardized differences (ASD) and p-value comparing patient characteristics between the two treatment cohorts and between each treatment cohort and the untreated cohort, where an ASD of at least 10% will be considered a meaningful difference. The secondary endpoint is the probability (estimated using propensity score) of receiving nintedanib vs. pirfenidone and that of receiving nintedanib or pirfenidone vs. no treatment based on patient characteristics; to identify baseline characteristics that drive initiation of a treatment while minimizing prescription bias.

These analyses will utilize real-world data to understand differences in patient characteristics between those prescribed nintedanib versus pirfenidone and those not receiving any antifibrotic treatments. The proposed data source, EMR data, allows exploration of several clinical characteristics (e.g., laboratory measures, medications, behavioral measures) in patients with IPF in a setting outside of a clinical trial.

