9.3 VARIABLES

9.3.1 Exposures

Both nintedanib (Ofev, BI) and pirfenidone (Esbriet, Genentech) were approved by the US FDA on October 15, 2014 (reflected by start of selection window in this study). Nintedanib initiators will be identified using prescription records for nintedanib, with the index date being the first prescription in the EMR during the selection window. Similarly, pirfenidone initiators will be identified using prescription records for pirfenidone; index date is first prescription. New users of these medications will be selected into the study, excluding those who initiated both medications on index. The number of patients who initiated both medications on index will be reported during the patient attrition. Since the purpose of this study is to identify predictors of IPF treatment initiation, no post-index follow-up measures will be reported. Patients who switched between the treatments during the pre-index period will be excluded because of the new user design, and those who switch after the index date will not be a concern as no study measures will be evaluated during the post-index period for the objectives of this study. No validation will be performed on the exposures of interest as exposure ascertainment relies on evidence of ≥ 1 prescription record.

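### Naming drivers of treatment choice by p<0.05 from a large, data-selected covariate pool can mix in many chance findings for nintedanib vs pirfenidone

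*Combined protocol and SAP*

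**What the plan says.** For the second objective, section 9.7.1 (Main analysis) plans multivariable logistic regression and propensity scores for nintedanib vs pirfenidone and for treated vs untreated. Covariates enter as follows: "possibly with stepwise selection) after controlling for key baseline characteristics (selected based on significance in bivariate analysis or face validity, e.g. age". Age is the only covariate named. The same paragraph says "Statistical tests will be two-sided, with" an alpha of 0.05, and lists c-statistics and ROC curves among the balance diagnostics. It gives no stepwise threshold, multiplicity adjustment or internal validation, and neither does any other section.

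For the primary objective, section 9.7.1 reports ASDs with 95% CIs and treats 10% or more as meaningful. It adds that the "p-value in comparing characteristics between the three cohorts will also be reported to help identify" key drivers of treatment selection.

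The secondary models serve two purposes. Section 9.1 states the endpoint, "The secondary endpoint is the probability (estimated using propensity score) of receiving nintedanib vs. pirfenidone", with a matching probability for either drug vs no treatment. It then states the aim: "to identify baseline characteristics that drive initiation of a treatment while minimizing prescription bias". Section 9.3.1 repeats that aim ("Since the purpose of this study is to identify predictors of IPF treatment initiation"), and section 7 says the study will "help identify patient characteristics driving the initiation of nintedanib or pirfenidone by assessing the probability of receiving the treatments". On numbers, the abstract says: "A preliminary analysis identified 868 IPF patients with pirfenidone, 615 patients with nintedanib, and about 10,000 untreated patients".

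**The concern.** Naming drivers is an intended output, so the rule by which a characteristic earns that name matters. Section 9.3.3 lists far more characteristics than a model of this size can sort reliably at p<0.05, and the plan does not fix which of them are candidates. Three effects can follow:

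- Null characteristics are named by chance.
- Real but modest differences that are kept because they reached p<0.05 look larger than they are.
- The c-statistic, fitted and evaluated on the same patients, suggests that treatment choice is more predictable than it is.

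A reader of the report could take a chance association as a prescribing pattern.

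**Working it through.** The plan states no power or error rate for this analysis beyond alpha 0.05, so there is no figure of its own to reproduce. Its counts do add up: Table 1, row 5a gives 868 + 615 + 144 = 1,627.

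**Inputs.** Preliminary counts are 615 (nintedanib), 868 (pirfenidone), hence 1,483 treated, and about 10,000 untreated. The number of candidates is my count from section 9.3.3, because the plan gives none:

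- 72 demographic, clinical, laboratory and lung-function items + 28 drug items + 11 non-drug items + 28 index-date drug items = 139.
- Without the index-date repeats: 111.
- Also without 5 overlapping items, 20 laboratory tests and 4 sparse lung-function tests: 82.
- I also use 50 as a low value.

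I assume 10 real drivers, each at ASD 10%, and all others null.

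**By hand, nintedanib vs pirfenidone.** The plan's SE at d = 0 is sqrt[(615 + 868)/(615 × 868)] = 0.0527.

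- Smallest ASD reaching p<0.05: 1.96 × 0.0527 = 0.103.
- Chance that a null covariate shows ASD of 10% or more: P(|Z| ≥ 0.10/0.0527 = 1.90) = 5.8%. The ASD threshold is thus no stricter than p<0.05 here, and it is not part of the entry rule for the models.
- Power for a true d of 0.10: 47.5%. Mean estimate given p<0.05: 0.144, or 1.44 times the truth.
- Expected nulls passing a 0.05 screen: 40, 72 or 129 × 0.05 = 2.0, 3.6 or 6.5. Expected real ones: 10 × 0.475 = 4.75.

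**Simulation of screening, then backward elimination at 0.05** (300 datasets per setting, independent binary covariates, new-data c from 3,000 + 3,000 patients):

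| Candidates | 50 | 82 | 139 |
|---|---|---|---|
| Chance drivers kept | 1.80 | 2.93 | 5.39 |
| Real drivers kept, of 10 | 4.36 | 4.47 | 4.40 |
| Chance share of those named | 29% | 40% | 55% |
| Log odds ratio ÷ truth, real drivers kept | 1.49 | 1.50 | 1.52 |
| Apparent c | 0.597 | 0.606 | 0.620 |
| c in new data | 0.550 | 0.547 | 0.542 |
| Excess | 0.047 | 0.059 | 0.078 |

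Repeat simulations gave 1.6–1.7, 2.9–3.2 and 5.2–5.6 chance drivers.

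**Sensitivity.**

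- Correlation of 0.3 or 0.6 in blocks of five: chance share 26–58%.
- Screening without stepwise: 1.77, 2.87 and 5.27 chance terms at p<0.05.
- Ten terms (5 real, 5 null) forced in on face validity: 1.80, 2.89 and 5.39.
- ASD 15%: chance share 1.70/9.50 = 18%, 2.90/10.66 = 27% and 5.01/12.72 = 39%; overstatement 15–17%; c excess 0.036–0.060.

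**What causes it.** Keeping every candidate and flagging p<0.05 names more chance drivers, not fewer (2.21, 4.03, 8.00). A fixed 30-term list containing all 10 real drivers flags about 1.0–1.1 nulls. Its estimates over all terms are only 1–3% too large, but those reaching p<0.05 are still 1.49 times the truth. Its c excess is 0.054–0.055 (0.04 with 20 terms, 0.07 with 40). A list alone therefore does not correct c, and naming by p<0.05 still overstates.

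**Treated vs untreated** (1,483 vs 10,000). The SE is 0.0278, so a null reaches ASD 10% with probability P(|Z| ≥ 3.59) = 0.03%. At true ASD 10%, selection from 50 or 139 candidates keeps 1.65 or 5.51 nulls beside about 9.5 of 10 real drivers. Overstatement is 4–5% and c excess 0.012–0.026. At ASD 15% overstatement is 1%.

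**The case against.** The best defence is that this is a descriptive study whose stated secondary endpoint is the propensity score, and that every characteristic is already tabulated with an unfiltered ASD and CI. That stands against any demand for strict multiplicity control. It would also be costly: a Bonferroni screen over 139 candidates cuts real drivers kept from 4.3 to 0.5 of 10. It does not dispose of the point, because sections 7, 9.1, 9.3.1 and 9.7.1 all make identifying drivers an aim, and the tabulated ASDs are unadjusted.

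Four stronger readings are tempting, and the documents do not support them.

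- A reader might infer that stepwise selection by p-value will be used. It is only a possibility, and face validity is another way in. Chance drivers can be named; the plan does not make that certain.
- A reader might infer that non-significant terms will be left out of the report. No section says so.
- A reader might infer that selection itself creates the chance drivers. The all-candidates result above shows otherwise.
- A reader might infer that the planned c-statistic is simply wrong. It is listed as a balance diagnostic, and for describing overlap of the fitted scores in this sample the apparent value is a fair summary. It misleads only if read as predictive ability, and the plan does not say which reading applies.

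The gain from a fixed list also depends on what it contains. If 3 of the 10 real drivers are left off, the chance share is 27% with 30 terms and 35% with 40. In the same run, selection from 50 and 82 candidates gave 28% and 41%.

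**Conclusion.** The point holds for nintedanib vs pirfenidone. With 10 real differences at ASD 10% and 50 to 139 candidates, roughly a quarter to a half of the drivers named by p<0.05 can be chance findings. Real effects kept for reaching p<0.05 can look about 1.5 times too large, and apparent c can exceed true predictive ability by about 0.05 to 0.08. The ASD threshold gives no protection in this comparison. The harm is smaller if real differences are larger.

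It does not carry over with the same force to treated vs untreated. There overstatement is small, and reading p-values together with the 10% ASD criterion removes nearly all chance findings.

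These sizes rest on preliminary counts, my own candidate count, equal real effects and complete data. The direction does not depend on the exact values. I rate this between something to consider and something that should be changed.

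**What to change.** In the second-objective text of section 9.7.1:

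- Replace significance screening and stepwise selection with a covariate list fixed on clinical grounds before any cohort comparison is seen. Keep it short: a 40-term list gains little and has c optimism of about 0.07.
- Report every model term with its estimate and 95% CI, whatever its p-value.
- Do not name drivers by p<0.05 alone, here or where bivariate p-values are used to identify key drivers. Label the drivers exploratory.
- Where a c-statistic is used to say how well characteristics predict treatment choice, give a bootstrap optimism-corrected value beside the apparent one. If any data-driven selection remains, repeat it inside each resample.

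The cost is SAP wording and modest programming, a longer table and a slightly lower reported c. Predictors left off the list appear only in the descriptive tables: if a 30-term list misses 3 of 10 real drivers at ASD 10%, about 3 reach p<0.05 instead of 4 to 5, and the reduction in chance findings is then small. About 5% of null terms on the list will still reach p<0.05. The bootstrap correction is approximate. For 30 terms at ASD 10% it moves c from 0.620 to 0.576, against 0.566 in new data; with no real drivers, from 0.580 to 0.523, against 0.501.
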